7.8.7. Safety Analyses

A Cox proportional hazards model will be used for the time to first cardiovascular event. HR and 95% CIs will be presented.

The ICD-10 diagnosis from the hospital claim and physician claim will be used to derive post-index myocardial infarction (MI) (I21.x, I22.x), stroke (I61.x – I63.x), or heart failure (I50.x, excluding I50.x2, I50.8x). Hospital discharge status code (20 to 29 or 40 to 42) will be derived for in-hospital death. A detailed code list is provided in [Appendix 3](#). Subjects with in-hospital cardiovascular death derived from indirect approach 2 ([Xie et al, 2018](#)) will be included in the analyses. 2018 ICD-10 CM and General Equivalence Mappings (GEMS) from the Centers for Medicare & Medicaid (CMS) ([will be used to translating ICD-9 CM to ICD-10 CM \(CMS, 2018\)](#)).

The As-Treated (AT) analysis will be conducted for the safety evaluation. The first incidence of a cardiovascular event after the index date and before the 30 days after the end of treatment will be analyzed.

A cardiovascular event is the first incidence of the composite endpoint of nonfatal MI, nonfatal stroke, or in-hospital cardiovascular death; the first incidence of the composite incidence of nonfatal MI, nonfatal stroke, heart failure or in-hospital cardiovascular death; or the first incidence of MI, stroke, heart failure, or in-hospital cardiovascular death separately.

7.8.8. Anabolic Drug Exposure

The overall duration of cohort anabolic drug exposure will be summarized for PS-matched patients.

Overall Duration of Anabolic Drug Exposure (day) = Date of last anabolic drug prescription fill + Supply days – index date + 1

Consecutive treatment duration is determined from the index date to the last drug supply date without any gap exceeding 60 days.

Because the efficacy and safety evaluations are limited to an 18-month period, the overall duration of the anabolic drug exposure will be cut off at 540 days, even if the patient used the anabolic drug (ABL or TPTD) for > 18 months.

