7.1.3. Limitations of the Study Design

There are several limitations associated with the design of the current study:

- The data source is administrative claims data, which are not collected for research purposes. Administrative claims data have inherent limitations including coding errors, inconsistencies, underestimation, overestimation, or incomplete diagnoses data. The current study, however, will use a claims-based algorithm to identify case qualifying (CQ) fragility fractures associated with osteoporosis. Furthermore, any misclassification of fractures is nondifferential between the treatment groups being compared and should not affect the results.
- Claims-based studies include potential inaccuracies related to the use of prescription medications. The prescription claim is for the date of first fill and not the date of first use of the medication, so the assumption is that these are the same date.

- Detailed clinical data such as BMD T-scores or the presence of other risk factors (eg, family history, smoking status, alcohol intake) associated with disease severity and increased future fracture risk are not available and, therefore, no adjustments have been made for these factors.
- Only deaths recorded on the hospital discharge status are available for the derivation of cardiovascular death in this study. The current study, however, will use a claims-based algorithm to identify deaths that are likely to be caused by cardiovascular events. Furthermore, any misclassification of deaths is nondifferential between the treatment groups being compared and should not bias the results.

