The comparative evaluation of treatment options is ideally done within the controlled clinical study setting. The current study is observational, and treatments are not assigned. As such, randomization is not possible. Although this is not a randomized study, PS matching will be used to define the study cohorts and provide confidence that the 2 treatment groups are comparable in their probability to receive and benefit from treatment. Patients will be matched on all indicators of disease severity and fracture risk including prior disease and treatment history. Furthermore, patients will also be matched on history of falls as well as comorbid conditions and concomitant medications associated with increased fall risk or with bone quality and strength. While several comorbidities were initially considered, some measures were ultimately not included in the end due to lack of available data. This includes duodenitis. Lastly, there could be residual confounding despite matching. The study is planned as an intention-to-treat (ITT) analysis for effectiveness evaluation and as-treated (AT) analysis for safety evaluation with additional consideration for duration of treatment exposure using sensitivity analyses on various length of observed treatment duration for the study cohorts. Interpretation is limited by the variable length of follow-up.

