7.6.7.2. Evaluation of Cardiovascular Safety

Evaluation of cardiovascular safety outcomes will be carried out for patients who have 18 months of follow-up data from their index date while on treatment with ABL or TPTD. The following data variables will be extracted:

- End of treatment date which is the last prescription date + supply day
- Date of the first incidence of MI
- Date of the first incidence of stroke
- Date of the first incidence of heart failure
- Date of in-hospital cardiovascular death
- Date of all-cause in-hospital death

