For the fracture outcomes, an ITT analysis will be applied. Patients will be followed for up to 18 months + 30-day follow-up, or until their first fracture event (for the fracture site of interest under evaluation) or in-hospital death, whichever comes first. Duration, in days, from the index date to the last follow-up date will be calculated. For calculation purposes, 1 month is equivalent to 30 days. All analyses are based on the patient's index medication cohort.

A nonvertebral fracture is any fragility fracture at the hip, pelvis, femur, ankle, shoulder (including shoulder, humerus, clavicle), radius/ulna, wrist, or tibia/fibula. Derivation details are provided in [Appendix 2](#).

The time to the first incidence of hip fracture and the other 7 individual fracture sites will be summarized using similar methods as those used for nonvertebral fracture.

The Kaplan-Meier curves will be generated to graphically display the fracture event or 18 months plus 30-day follow-up.

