7.8.10. Sensitivity Analyses

7.8.10.1. Population Selection

To evaluate the stability of the PS matched cohorts, 2 different calipers (0.15, 0.3) will be carried out to the PS matching. The sensitivity analyses on effectiveness and safety endpoints will be performed on these matching populations.

Sensitivity analyses on effectiveness and safety endpoints will be performed on sub population with each of additional exclusion criteria:

- Exclude patients without a minimum of 12 months of anabolic drug exposure:
 - (1) 12-consecutive months of anabolic drug exposure as assessed by medication dispensed; and
 - (2) 12-month cumulative anabolic drug exposure during the 18-month follow-up
- Exclude patients with prescriptions dispensed for \leq 1 month, 3 months, 6 months, and 9 months
- Exclude patients with previous use of denosumab or zoledronic acid

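### The exposure formula in 7.8.8 counts one day too many, which could keep patients at an exact month limit in the sensitivity analyses of 7.8.10.1 if those limits use this duration

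*Combined protocol and SAP*

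**What the plan says.** Section 7.8.8 gives one explicit formula for drug exposure: "Overall Duration of Anabolic Drug Exposure (day) = Date of last anabolic drug prescription fill + Supply days", minus the index date, plus 1. The result is capped: "the overall duration of the anabolic drug exposure will be cut off at 540 days". The same section also describes a consecutive duration that tolerates gaps of up to 60 days, but gives no day-count formula for it.

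Three other places bear on the count:

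- Section 7.1.3, on the date of first fill and the date of first use: "so the assumption is that these are the same date".
- Section 7.6.7.2 lists the "End of treatment date which is the last prescription date + supply day". It does not say whether that date is the last day with drug or the first day without it.
- Section 7.8.6: "For calculation purposes, 1 month is equivalent to 30 days".

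Section 7.8.10.1 then plans an exclusion that begins "Exclude patients with prescriptions dispensed for" and goes on to at most 1, 3, 6 and 9 months. It does not say which variable measures this. Section 7.1.3 describes the purpose as "sensitivity analyses on various length of observed treatment duration for the study cohorts", and Table 1 likewise marks the prescription-fill criterion as one to be restricted further by length of treatment.

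**The concern.** Adding 1 to a difference of dates is correct when both dates are days to be counted. If the fill day is day 1 of treatment, a supply of s days runs out at the end of day s, whose date is fill + s - 1. The date fill + s is the first uncovered day, so the formula includes a day for which no drug was dispensed.

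One day is trivial in a summary of exposure. It can matter where a limit falls on a whole number of supply periods. With 30-day months, the limits in 7.8.10.1 are 30, 90, 180 and 270 days, which are also the spans of 1, 3, 6 and 9 back-to-back 30-day fills. If the 7.8.8 duration drives the exclusions, patients exactly at a limit move from excluded to kept. Single-fill patients are the group most clearly meant to drop out at the first limit.

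**Working it through.** **Inputs.** Formula and 540-day cap: 7.8.8. Fill day equals day of first use: 7.1.3. One month equals 30 days: 7.8.6. Limits of at most 1, 3, 6 and 9 months: 7.8.10.1, reading the less-or-equal sign as applying to all four. Supply per fill is **not in the documents**; I assume 30 days and check 28 to 31.

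**The plan's own figure.** 18 months × 30 days = 540 days, which reproduces the cap. Eighteen back-to-back 30-day fills supply exactly 540 days. The last fill is on day offset 17 × 30 = 510, so the formula gives 510 + 30 - 0 + 1 = 541. The cap cuts this to 540 and hides the extra day there, but not at shorter durations.

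**Single fill on the index date.** The formula gives 0 + s - 0 + 1 = s + 1. The direct count of covered days is s.

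| Supply (days) | Formula | Direct count | At most 30 by formula? | At most 30 by direct count? |
|---|---|---|---|---|
| 28 | 29 | 28 | yes, excluded | yes, excluded |
| 29 | 30 | 29 | yes, excluded | yes, excluded |
| 30 | 31 | 30 | no, kept | yes, excluded |
| 31 | 32 | 31 | no, kept | no, kept |

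Only the fill of exactly 30 days changes status.

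**Back-to-back fills.** With n fills of s days, the last fill is at offset (n - 1)s, so the formula gives ns + 1 against a direct count of ns.

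| Fills | Limit (days) | 30-day fills: formula / direct | 28-day fills: formula / direct |
|---|---|---|---|
| 3 | 90 | 91 / 90 | 85 / 84 |
| 6 | 180 | 181 / 180 | 169 / 168 |
| 9 | 270 | 271 / 270 | 253 / 252 |

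The 30-day pattern changes status at each limit. The 28-day pattern does not.

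**How narrow this is with several fills.** The overall duration spans gaps. Take three 30-day fills with refills one day late in total: the last fill is at offset 61, so the span is 61 + 30 = 91 without the added 1 and 92 with it, and the patient is kept either way. With refills one day early in total, the last fill is at offset 59, giving 89 and 90, and she is excluded either way. The status changes only when the span is exactly 90, 180 or 270 days.

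**The 12-month minimum in 7.8.10.1.** Twelve back-to-back 30-day fills give 361 against 360. Both meet a 360-day minimum. If that rule used this duration, only a true 359 days would change status.

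**The case against.** The strongest reply is that the consequence is not written in the plan. A reader might infer that a patient with one 30-day fill does escape the 1-month exclusion. The documents do not support that as a fact. Section 7.8.10.1 speaks of prescriptions dispensed, which can be read as total days' supply; then 30 is at most 30 and she is excluded as intended. Section 7.8.8 introduces the overall duration for a descriptive summary, and the consecutive duration is a further candidate. So it would also be wrong to call the overall duration the only one that the plan defines. It is the only one with an explicit formula, and the emphasis on treatment duration in 7.1.3 and Table 1 makes it a natural choice, but not a stated one.

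A reader might also infer that the extra day would remove single-fill patients from one cohort only. That needs a difference between the products in supply per fill, and the documents give no figure from which to check it.

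A third reply is that if the end-of-treatment date in 7.6.7.2 is taken as the last treatment day, end minus start plus 1 is an ordinary inclusive count. This does not rescue the formula. With first use on the fill date, a 30-day supply ends at offset 29. If first use were instead the next day, supply would last to offset 30, but the index day would then have no drug. Either way 30 days of supply are counted as 31. What does stand is that the convention is shared with 7.6.7.2, so editing 7.8.8 alone would leave it half stated.

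The narrowness with several fills, shown above, also stands.

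**Conclusion.** The one-day overcount is established from the plan's own rules and does not depend on the supply length, although the cap masks it at 540 days. The effect on the 1-, 3-, 6- and 9-month exclusions is conditional on 7.8.10.1 using the 7.8.8 duration and on a span falling exactly on a limit. In practice that means mainly single fills of exactly 30 days. How many patients this concerns, and whether the cohorts would be affected unequally, cannot be determined from the documents.

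The primary intention-to-treat fracture analysis does not use this duration and is unaffected. The exposure summary is off by at most one day per patient. This is a minor point, worth correcting because it can decide who is excluded at a boundary and because a programmer must otherwise choose the variable without guidance.

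**What to change.** 1. In 7.8.8, drop the + 1. Equivalently, define the last covered day as last fill date + supply days - 1 and keep the + 1.
2. In 7.6.7.2, use the same end-date convention and say whether the end-of-treatment date is the last covered or the first uncovered day. The as-treated window in 7.8.7 is counted from that date, so its last day should be checked against the chosen wording.
3. In 7.8.10.1, state that the 1-, 3-, 6- and 9-month limits use the corrected overall duration, with 1 month equal to 30 days.

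The cost is a small edit to the plan and program, with no new data. Reported exposure falls by one day, except for patients still at the 540-day cap.

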7.8.9. Concomitant Use of Osteoporosis Treatment

Between the index date and the end of the Treatment Period (18 months + 30-day follow-up period), use of any osteoporosis treatment options other than ABL or TPTD will be summarized for the PS-matched populations.

7.8.10. Sensitivity Analyses

7.8.10.1. Population Selection

To evaluate the stability of the PS matched cohorts, 2 different calipers (0.15, 0.3) will be carried out to the PS matching. The sensitivity analyses on effectiveness and safety endpoints will be performed on these matching populations.

Sensitivity analyses on effectiveness and safety endpoints will be performed on sub population with each of additional exclusion criteria:

- Exclude patients without a minimum of 12 months of anabolic drug exposure:
 - (1) 12-consecutive months of anabolic drug exposure as assessed by medication dispensed; and
 - (2) 12-month cumulative anabolic drug exposure during the 18-month follow-up
- Exclude patients with prescriptions dispensed for \leq 1 month, 3 months, 6 months, and 9 months
- Exclude patients with previous use of denosumab or zoledronic acid

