7.6.7.1. Evaluation of Effectiveness

A claims-based algorithm with high specificity for fracture site developed by Wright et al ([Wright et al, 2019](#)) will be used to identify osteoporosis-related fractures (see Appendix 2). Case qualifying (CQ) fractures are those identified during an inpatient hospital stay, in any position on the medical claim, or in an outpatient setting accompanied by a fracture repair procedure code. Validation of this algorithm was done using International Classification of Diseases, 9th Revision (ICD-9) codes before the Healthcare System in the USA switched to the ICD-10 system. In a separate study, Wright et al mapped the ICD-9 codes to ICD-10 codes in an evaluation of hip fracture trends in the Medicare data. The results from that study did not suggest that the ICD-10 version systematically identified a higher or lower number of fractures than the ICD-9 codes.

The evaluation period for nonvertebral fracture events will start from the index date (date of initial prescription dispensed) to the earliest of the following events:

- a) First non-vertebral fracture event date (hip, pelvis, shoulder, radius or ulna, wrist, femur, tibia or fibula, ankle)
- b) 18 months after the index date
- c) In-hospital death

The evaluation period for hip fracture events will start from the index date (date of initial prescription dispensed) to the earliest of the following events:

- a) first hip fracture event date
- b) 18 months after index date
- c) In-hospital death

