7.8.3. Analysis Populations

Analysis population are all patients meeting the study inclusion/exclusion criteria and selected after propensity matching. The same matched population will used for both effectiveness and safety analysis.

The effectiveness evaluation will be conducted using an ITT analysis, meaning that the first fracture event during the 18 months (+ 30 days follow-up) after the index date will be summarized regardless of when treatment ended. Cardiovascular safety outcomes will be evaluated using an As-Treated (AT) analysis based on only events occurring during the treatment period which is from the index date to the last prescription anabolic drug obtained within the 18 months after the index date, regardless of the anabolic drug possession gap between any 2 prescription fills.

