7.8.6. Effectiveness Analyses

In this study, the primary analyses of effectiveness will be noninferiority analyses for ABL versus TPTD on time to the first incidence of nonvertebral fractures with a margin of 30%. Noninferiority of ABL to TPTD will be concluded if the upper bound of 2-sided 95% CI of HR between ABL versus TPTD is < 1.3.

In a recently published historical control observational study evaluating the real-world effectiveness of osteoporosis therapies using Medicare claim data between 2008 and 2011, the fracture incidence rates for the 12-month pre-treatment period were compared with the 12-month on-treatment period ([Yusuf et al, 2018](#)). For patients treated with TPTD, the incidence rate ratio (IRR [95% CI]) was 0.36 (0.31 to 0.41) for any fracture and 0.34 (0.32 to 0.36) for hip fracture. Based on the EMA and FDA noninferiority margin guidelines ([EMA, 2005](#); [FDA, 2016](#)), if the upper boundary of ABL versus TPTD is $HR < 1.3$, then ABL will preserve approximately 70% of the TPTD benefit, which is higher than the minimum required threshold of 50%.

Comparisons of the time to fracture between the PS-matched ABL and TPTD groups will be based on a Cox proportional hazards model. The hazard ratio (HR) and 95% confidence interval (CI) between the 2 treatment groups will be calculated. The Kaplan-Meier method will be used to estimate event rates. Log rank test will be calculated.

For the fracture outcomes, and the corresponding sensitivity and subgroup analyses, patients will be followed for up to 18 months or until their first fracture event (for the fracture site of interest under evaluation), whichever comes first. All analyses are based on index medication cohort.

The duration, in days, from the date of the first filled prescription for ABL or TPTD to the first incidence of nonvertebral fracture will be derived. If a patient does not experience any nonvertebral fractures during the 18 months of treatment + 30-day follow-up (for a total of 19 months), the patient will be censored at the day of in-hospital death or the 19 months.

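### The exposure-restricted fracture sensitivity analyses select women on drug dispensed after index but count fractures from index, and no on-treatment fracture analysis is planned beside them

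*Combined protocol and SAP*

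**What the plan says.** Section 7.8.10.1 states: "Sensitivity analyses on effectiveness and safety endpoints will be performed on sub population with each of additional exclusion criteria". One criterion is to "Exclude patients without a minimum of 12 months of anabolic drug exposure", counted as consecutive and then as cumulative months. Another begins "Exclude patients with prescriptions dispensed for" and lists 1, 3, 6 and 9 months or less.

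Section 7.8.8 measures overall exposure from index to "Date of last anabolic drug prescription fill + Supply days". For the consecutive version, "Consecutive treatment duration is determined from the index date to the last drug supply date without any gap exceeding 60 days". Both are known only after index.

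The fracture clock starts earlier. Section 7.6.7.1 says "The evaluation period for nonvertebral fracture events will start from the index date (date of initial prescription dispensed". Section 7.8.6 carries the same clock over: "For the fracture outcomes, and the corresponding sensitivity and subgroup analyses, patients will be followed for up to 18 months". For fracture the plan gives no landmark, delayed entry or censoring at the end of treatment. Under Section 7.8.3, "the first fracture event during the 18 months (+ 30 days follow-up) after the index date will be summarized regardless of when treatment ended".

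Sections 7.1, 7.8.3 and 7.8.7 assign as-treated analysis to cardiovascular safety only. Section 7.1.3 offers the exposure-length analyses as the plan's way of taking treatment duration into account, and does not mention this selection.

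**The concern.** Membership of each restricted set depends on what happens during follow-up, and a fracture can itself end treatment. A woman who fractures in month 4 and stops leaves the 6-, 9- and 12-month sets together with her event. A woman who fractures in month 4 and continues stays in. Each set therefore loses early fractures selectively, and more of them as the cut-off rises.

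What is at stake is interpretation. A reader will use these analyses to ask whether the ITT result holds in women who stayed on drug. The HR could drift up or down with longer exposure for reasons that have nothing to do with the drug. No on-treatment fracture result is planned against which to check it.

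**Working it through.** The plan gives no figure for these analyses, so there is none to reproduce.

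**Inputs from the documents.** Fracture rate 3.5% at 18 months, 8,000 women per cohort and margin 1.3 (Section 7.8.1.2); follow-up of 18 months plus 30 days, that is 570 days (Section 7.8.6); the exposure rule of Section 7.8.8.

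**Assumptions.** Constant hazard; fills every 30 or 90 days, on time; permanent stopping; 50% persistence at 12 months; true HR 1.3. The share of women who stop because of a fracture is qA = 40% on abaloparatide and qT = 20% on teriparatide.

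**Fracture-triggered stopping.** Let c be the day of the last fill a woman needs in order to stay in the set, counting days supplied. A fracture before day c that stops treatment removes her. The share of fractures before that day is about s = c/570, so

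restricted HR ≈ true HR × (1 − qA·s) / (1 − qT·s).

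Background stopping unrelated to fracture cancels. At 12 months with 30-day fills, c = 330 and s = 330/570 = 0.579, giving 1.3 × 0.768/0.884 = 1.13. With 90-day fills, c = 270 and s = 270/570 = 0.474, giving 1.3 × 0.811/0.905 = 1.16. Simulation agrees within its Monte Carlo error of about 0.4–1%:

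| Cut-off (months) | c, 30-day fills | Formula | Simulated | c, 90-day fills | Formula | Simulated |
|---|---|---|---|---|---|---|
| 1 | 30 | 1.29 | 1.28 | 0 | 1.30 | 1.30 |
| 3 | 90 | 1.26 | 1.25 | 90 | 1.26 | 1.25 |
| 6 | 180 | 1.21 | 1.21 | 180 | 1.21 | 1.21 |
| 9 | 270 | 1.16 | 1.16 | 270 | 1.16 | 1.16 |
| 12 | 330 | 1.13 | 1.13 | 270 | 1.16 | 1.16 |

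With 90-day fills the 9- and 12-month sets are the same women.

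- *Reversed (20% vs 40%), 12 months:* 1.3 × 0.884/0.768 = 1.50 and 1.3 × 0.905/0.811 = 1.45; simulated about 1.49 and 1.45.
- *Equal stopping (30% each):* the ratio of brackets is 1 and the HR stays at about 1.30 at every cut-off. The 12-month set still loses 0.3 × 0.579 = 17% or 0.3 × 0.474 = 14% of its fractures. Teriparatide risk reads 3.1–3.2%, against 1 − 0.965^(570/540) = 3.7% in the full cohort.
- *Equal stopping without proportional hazards:* some shift remains. Take a true HR of 1.5 before month 12 and 1.0 after, with half of early fractures stopping treatment in both cohorts. A full-cohort ratio of 1.33 then reads 1.25.
- *Persistence of 30–70%:* the 12-month value moves by about 0.01.
- *Follow-up of 540 days:* s = 330/540 = 0.611, and the 12-month value is 1.3 × 0.756/0.878 = 1.12.
- *The extra day in the Section 7.8.8 formula, applied literally:* a woman with exactly 1, 3, 6 or 9 months supplied is kept. The simulated values from 1 to 12 months become 1.30/1.27/1.22/1.18/1.13 (30-day fills) and 1.30/1.30/1.26/1.22/1.17 (90-day fills).

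**Risk-related stopping.** In a second simulation the true HR was 1.0 and no stopping was triggered by fracture. Thirty percent of women were frail with 3.5 times the fracture hazard, and frail abaloparatide women stopped faster than the rest.

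| 12-month comparison | Twice as fast | 1.5 times as fast |
|---|---|---|
| Restricted, from index | 0.83–0.86 | 0.92–0.93 |
| Landmark | 0.82–0.86 | 0.92–0.93 |
| On-treatment (not restricted) | 0.91–0.92 | 0.96 |

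ITT stays at 1.00. If frail women stop twice as fast in both cohorts, every HR is 1.00–1.01.

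**The case against.** The strongest reply is that the HR moves only if stopping differs by cohort, and nothing in the documents shows that it does. Section 6.3 describes new users of the two drugs as similar in disease characteristics. This stands as a limit on size. Similarity at initiation does not settle why women stop later, so it does not close the question.

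The illustration is also simple. It has no pauses and every stop is permanent, whereas a woman who pauses after a fracture and resumes could stay in the cumulative 12-month set. That stands too. ITT for effectiveness is a deliberate choice, and adding an on-treatment companion is partly preference; but the plan itself offers a look at duration, and this one is hard to read.

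Three stronger readings are tempting.

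- A reader might infer that the selection undermines the noninferiority conclusion. It does not: the primary test is ITT in the full matched population, and no noninferiority rule is attached to these analyses.
- A reader might infer that the design favours abaloparatide. Both cohorts are restricted by the same rule, and the illustration runs either way.
- A reader might infer that the restricted sets are left unmatched, because Section 7.8.11 matches each subgroup separately and Section 7.8.10.1 does not say so. However, Table 1 lists treatment duration as a sensitivity variation of the prescription-fill criterion, and Section 7.8.5 matches all patients who meet the criteria. Together these point to restriction before matching. One confirming sentence is enough.

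**Conclusion.** The point holds for the fracture sensitivity analyses restricted by exposure. As written, they condition on the future and can remove a fracture together with the woman it caused to stop. Under the assumed 40% vs 20% stopping, a true HR of 1.3 is displaced modestly at 1–3 months, by up to about 0.05, and by about 0.14–0.17 at 12 months. The opposite pattern raises it by about 0.15–0.19. Stopping that is equal by cohort leaves the HR about right under proportional hazards and understates event rates. All stopping and persistence figures are assumptions, so these numbers show what could happen and do not predict it.

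The primary ITT noninferiority test and the primary as-treated safety analysis are untouched, and no study decision rests on the restricted analyses. The harm is to interpretation of the duration analyses. The change is worth making because it is cheap.

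**What to change.** 1. Add a supportive on-treatment fracture analysis in the full matched cohort. Start at index and censor at the earliest of 30 days after the end of consecutive treatment (the 60-day gap rule of Section 7.8.8), in-hospital death, or 18 months plus 30 days. State that this differs from the safety as-treated rule, which runs to the last fill whatever the gaps. Repeat it with a 60-day extension, because whether a gap exceeds 60 days is known only after 60 days.
2. Start the 6-, 9- and 12-month restricted fracture analyses at day 180, 270 and 360, in women event-free and still exposed. Label them descriptive.
3. Confirm in one sentence that matching follows each restriction.

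The work is SAP wording and some programming, with no new data. The statistical cost is events. The figures below take a true HR of 1 and 50% persistence, with 95% CI = exp(±1.96 × 2/√events).

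| Analysis | Events | CI around HR 1 |
|---|---|---|
| ITT | 16,000 × 3.69% = 590 | 0.85–1.18 |
| On-treatment | 390–411 (304–484 for 30–70% persistence) | about 0.82–1.22 |
| 6-month landmark | 300–339 | |
| 9-month landmark | 193–218 | |
| 12-month landmark | 114–128 | about 0.69–1.44 |

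Both changes remove the fracture-triggered route; simulated HRs stay at 1.28–1.31 when the truth is 1.3. Neither cures stopping by frailer women that differs by cohort. In the second simulation on-treatment censoring removed about half of the shift and the landmark none. Adjustment can help only in part, because bone density, smoking and family history are unavailable (Section 7.1.3).
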